## **7. STUDY POPULATION**

### **7.1. Subjects Disposition**

The disposition of all subjects will be summarized by cohort and site. Subject disposition tables will include the number and percent of subjects who were:

- included in each analysis populations (Safety, Evaluable);
- discontinued from the study early, summarized by primary reason for discontinuation.

The number of subjects screened and number of days in the study of each subject will also be summarized by cohort and overall.

Frequency and percentages of patients completing and discontinuing the study prior to the primary endpoint (Study Day 60) and prior to the last study visit (Study Day 180) will be analyzed by cohort and overall.

### **7.2. Protocol Deviations**

At the discretion of the sponsor, major protocol violations as determined by a review of the data of the study results and the conduct of statistical analyses may result in the removal of a subject's data from the PP Populations. The sponsor, or designee, will be responsible for producing the final protocol violation file. This file will include a description of the protocol violation, and clearly identify whether or not this violation warrants exclusion from the Evaluable Population.

All protocol deviations by type of deviations will be summarized by cohort and overall.

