12.2. Analysis Populations

The 2 analysis populations are defined in the study's Statistical Analysis Plan (SAP) as follows:

- Safety Population: All patients who sign informed consent for the study, complete baseline assessments, and receive at least 1 dose of XADAGO.
- Evaluable Population: All patients in the safety population who complete at least the MDS-UPDRS assessment at the Study Day 60 visit.

The principal analysis of the primary endpoint will be conducted for the evaluable population. Sensitivity analysis of the primary endpoint will be carried out for the safety population. Safety summaries will be provided for the safety population.

Eligible, consented, and enrolled study participants will be analyzed based on concomitant PD medication regimen change at Baseline:

Cohort A – Patients that have switched to XADAGO from a Dopamine Agonist

Cohort B – Patients that have switched to XADAGO from an MAO-B inhibitor

Cohort C – Patients that are MAO-B inhibitor naïve

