## 2. INTRODUCTION

The purpose of this statistical analysis plan (SAP) is to describe the planned analyses and data displays to be included in the Clinical Study Report (CSR) for Protocol USWM-SA1-4001.

Protocol Revision Chronology:		
Protocol	28-AUG-2017	Original
Protocol	01-NOV-2017	Amendment 1
Protocol	12-OCT-2018	Amendment 2

This SAP was developed in accordance with ICH E9 guidelines. All decisions regarding final analysis, as defined in this SAP document, will be made prior to Database Freeze (unblinding) of the study data. Further information can be found in the protocol.

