## **5. PLANNED ANALYSES**

### **5.1. Interim Analyses**

Interim data analyses will be performed periodically to provide study updates and to support potential presentation of interim results

. Since this study is observational only and treatments are not assigned to specific patient/treatment groups, these interim analyses will have no statistical implications.

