#### **6.5.4. Evaluable Population**

The Evaluable population comprises all subjects in the safety population who complete at least the MDS-UPDRS assessment at the Study Day 60 visit. Evaluable population will be used to analyze MDS-UPDRS endpoint.

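### SAP 7.2 permits discretionary, results-informed exclusion from the Evaluable Population, which SAP 6.5.4 and Protocol 12.2 define by Day 60 MDS-UPDRS completion alone

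*SAP*

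**What the plan says.** SAP 6.5.4 gives a single membership rule: "The Evaluable population comprises all subjects in the safety population who complete at least the MDS-UPDRS assessment at the Study Day 60 visit". It adds that "Evaluable population will be used to analyze MDS-UPDRS endpoint". Protocol 12.2 defines the set in the same way and states that "The principal analysis of the primary endpoint will be conducted for the evaluable population". Neither section contains an exclusion for protocol deviations.

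SAP 7.2 contains one. Its first sentence makes removal a matter of sponsor discretion, for major violations that, in its words, "as determined by a review of the data of the study results and the conduct of statistical analyses may result in the removal"; what is removed is the patient's data. The sentence ends by naming PP Populations. PP is in the SAP's abbreviation list, but no such population is defined in SAP 6.5. The paragraph then makes the sponsor or its designee responsible for a final violation file, which must "clearly identify whether or not this violation warrants exclusion from the Evaluable Population". Neither document lists the violations that count as major.

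Three other statements bear on timing and safeguards. SAP 2 says that decisions on the final analysis "will be made prior to Database Freeze (unblinding) of the study data". SAP 5.1 says that "Interim data analyses will be performed periodically to provide study updates". Protocol 12.2 says that "Sensitivity analysis of the primary endpoint will be carried out for the safety population"; the SAP does not repeat this.

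**The concern.** The SAP gives two routes to the analysis set for MDS-UPDRS. One is mechanical: Safety-population membership and a completed Day 60 MDS-UPDRS. The other adds a judgement by the sponsor, on criteria that are not written down, and the section that describes it refers to reviewing results and analyses. Two programmers working from this SAP could build different sets.

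The study has no control arm, so the mean change from baseline is itself the result. If patients who worsened are more likely to have a deviation classed as major, the mean moves towards improvement and the paired t-test of SAP 8.4 no longer has its nominal 5% level. In a randomised, blinded trial, exclusions decided before unblinding would be made without knowledge of treatment group. Here there is no comparator and no described blind, so that protection is not available.

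**Working it through.** **1. Does the exclusion reach the Evaluable Population?** The sentence about reviewing results names PP Populations; the sentence about the violation file names the Evaluable Population. They stand in one paragraph on one process, and the SAP defines no PP set to which the first could apply. SAP 7.1 lists only Safety and Evaluable for the disposition table. The file's power to exclude from the Evaluable set is therefore explicit. That the exclusion may rest on study results is a reading of the paragraph as a whole, and a natural one.

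**2. Does SAP 2 close the gap?** SAP 5.2 runs the final analyses after database lock. A decision that draws on the conduct of analyses must then either come after the freeze, against SAP 2, or draw on interim output. SAP 2 equates the freeze with unblinding, but SAP 4.4 says that the study is not randomised, Protocol 12.3 says that it assigns no treatment, and neither document describes a blind.

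**3. Illustration of size.** The documents give no SD, effect size or power calculation, so there is no plan figure to reproduce.

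- From the documents: n = 540, the planned maximum (SAP 4.3.1); paired t-test (SAP 8.4); two-sided 5% level (SAP 6.4).
- Assumed: true mean change 0, SD 1, normal; 5%, 10% or 20% of patients are violators, unrelated to outcome; the half of the violators with the worst change are removed.

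The results come from 20,000 simulated trials per row:

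| Violators | Removed | Left | Shift of mean (SD) | Type I error |
|---|---|---|---|---|
| none | 0 | 540 | 0.00 | 0.049 |
| 5% | 14 | 526 | -0.020 | 0.074 |
| 10% | 27 | 513 | -0.041 | 0.152 |
| 20% | 54 | 486 | -0.088 | 0.491 |

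Negative means towards improvement. When 27 of 540 are removed without regard to outcome, the type I error is 0.051.

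Hand check of the 10% row. The worse half of a normal sample has mean √(2/π) = 0.798 SD. Removing 27 such patients shifts the remaining mean by about 27 × 0.798 / 513 = 0.042 SD. The SE is 1/√513 = 0.0441, so the simulated shift is 0.041 / 0.0441 = 0.93 SE. The rejection probability is about Φ(-1.96 + 0.93) + Φ(-1.96 - 0.93) = 0.151 + 0.002 = 0.153, in agreement with 0.152.

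For a cohort of 180 (three equal cohorts, an assumption), removing 4, 9 or 18 patients under the same rule gives type I errors of 0.057, 0.081 and 0.196.

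**4. Upper bound.** If the worst fraction p of all patients were removed, the shift would be φ(z)/(1 - p), where z is the upper p quantile:

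- p = 2%: 0.0484 / 0.98 = 0.049 SD
- p = 5%: 0.1031 / 0.95 = 0.109 SD
- p = 10%: 0.1755 / 0.90 = 0.195 SD

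This would require every patient with a poor outcome to be a violator. SAP 7.2 allows removal only for a violation, so these figures are a ceiling and not an expectation.

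**The case against.** The strongest reply is that SAP 7.2 is stale template text. The SAP has other carry-over: an abbreviation for a transdermal placebo, a baseline rule for laboratory values, and a per-protocol table title offered as an example in SAP 6.2. The results-review sentence itself names a population that does not exist. This stands as a probable explanation of how the wording arose. It does not remove the conflict, because the violation-file sentence names a population that does exist.

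Second, SAP 2 places decisions before the freeze. That is a real constraint, though a weak one in an unblinded study with periodic interim analyses. It also cannot be said that the people judging violations will know the MDS-UPDRS changes: neither document states what the interim outputs contain or who sees them.

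Third, exclusions would leave traces. SAP 6.2 provides a table series for reasons for exclusion from efficacy, SAP 7.1 reports the size of each population, and SAP 7.2 summarises all deviations by type. The Safety-population sensitivity analysis in Protocol 12.2 would partly expose selection. The SAP does not cancel it, but does not plan it either. It would not be a clean comparison, since the SAP imputes missing efficacy data by LOCF (SAP 6.8.1), and by the schedule the only MDS-UPDRS before Day 60 is the baseline one.

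Fourth, the study is descriptive, with no decision rule. This limits the consequences, but the SAP still plans significance tests at 5%.

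**Conclusion.** The point holds as a conflict between SAP 7.2 and the definition in SAP 6.5.4 and Protocol 12.2, and as a permission for outcome-aware exclusion in the SAP's only MDS-UPDRS set. It should be fixed.

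A reader might infer that the MDS-UPDRS result has been or will be selected on outcome, or that the t-test is already invalid. The documents do not support this: they allow such exclusion but show neither its use nor any intention to use it, and the test loses its level only if the discretion is exercised with knowledge of outcome. A reader might also extend the point to all primary outcomes. Under SAP 6.5.3, PDQ-39 and MoCA are analysed in the ITT set, which SAP 7.2 does not touch.

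The size, a shift of about 0.02 to 0.09 SD and a type I error of about 0.07 to 0.49, rests on assumed violation rates of 5% to 20% and an assumed rule of removing the worst half of violators. None of these is in the documents.

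**What to change.** - Delete the exclusion wording from SAP 7.2, including the reference to PP Populations. State that deviations are listed and summarised only, and that Evaluable membership is fixed by SAP 6.5.4.
- Carry the Safety-population sensitivity analysis of Protocol 12.2 into the SAP for MDS-UPDRS.
- If a deviation-based set is wanted, define it as a separate sensitivity set with a closed list of deviations, judged by people without access to outcome data. Disclose any interim output already seen when the list is fixed; the documents do not show whether any exists.

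The first item costs only SAP wording. The second adds one analysis that the protocol already promises. The third, if chosen, also needs a reviewer kept apart from the outcome data.

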### **7.3. Demographic and Baseline Characteristics**

All subjects in the safety population are included in the post text table which summarizes the subject population, and for all treated subjects by cohort and overall, with respect to age at entry into the study, age at onset of the condition under study, sex, race, weight, height, body temperature, any primary diagnostic criteria and/or secondary co-morbid diagnoses.

Age will be reported in years and summarized with descriptive statistics N, mean, s.d., median, and range (e.g., minimum and maximum values), and as a frequency distribution in the groups of 30-<65 and >65 years.

### **7.4. Medical History Present at Entry**

Medical history information will be coded using the latest MedDRA dictionary and summarized by treatment (50 mg vs 100 mg), by cohort and overall for the safety population using descriptive statistics. No formal statistical comparisons will be performed.

### **7.5. Prior Medication History and Medications Present at Entry**

Prior medication is defined as the medications stopped before the first dose date. Prior medications taken during the study will be coded using the latest WHO Drug dictionary and will be summarized by ATC level 2, ATC level 4 and preferred term for each cohort and overall.

A by-subject listing of prior medication data will be presented.

## **8. EFFICACY**

### **8.1. Testing Statistical Assumptions Including Comparability at Baseline**

For baseline data, univariate statistics will be generated for continuous data (e.g., age, height, weight, body temperature, the efficacy assessment scales, subscales, and factors) in order to examine the nature of the underlying statistical distributions and identify the extent to which outliers affect the distributions.

### **8.2. Subgroup Analyses**

No subgroup analyses will be done in this study.

### **8.3. Multiple Comparisons and Multiplicity**

No multiplicity issue in this study.

### **8.4. Analysis of the Efficacy Endpoint**

The change in MDS-UPDRS, PDQ-39, and MoCA from the Baseline Assessment Visit to the Primary Endpoint (Study Day 60) will be summarized by cohort and overall. An analysis of paired t-test will be used to analyze the continuous endpoints.

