XADAGO was evaluated in two double-blind, placebo-controlled, multinational, 24-week studies. In both studies, change in *on* time without dyskinesia plus *on* time with non-troublesome dyskinesia, as determined by patient diary, was the primary endpoint. Secondary endpoints included change in *off* time and clinician-rated change in Movement Disorders Society - Unified Parkinson's Disease Rating Scale (MDS-UPDRS) Part III scores. The trials were conducted in patients with PD who had at least 1.5 hours of daily *off* time, despite optimized treatment regimens of levodopa/carbidopa. Patients could also be taking dopamine agonists, catechol-O-methyl transferase (COMT) inhibitors, anticholinergics, and amantadine. In Study 1, patients were randomized to placebo, 50 mg/day or 100 mg/day of XADAGO. In Study 2, patients were randomized to placebo or a treatment group in which all patients were started on 50 mg/day for 2 weeks, then increased to 100 mg/day thereafter (Borghain, 2014a; Schapira, 2017). Both studies showed significant improvements in *on* time without troublesome dyskinesia as compared to placebo, as well as significant decreases in *off* time and improvement in UPDRS Part III scores (Borghain, 2014a; Schapira, 2017). The improvements in *on* time and *off* time seen at 6 months were maintained out to 2 years in an 18-month extension of Study 1 (Borghain, 2014b). Both the 50 mg/day and 100 mg/day doses of XADAGO were well tolerated by patients and had safety profiles similar to that of placebo. The most commonly reported adverse event (AE) was dyskinesia, which was significantly higher in the treatment groups versus placebo. Of the patients who discontinued due to an AE, 1% of patients in the treatment group discontinued due to dyskinesia and 0% in the placebo group. In addition to the clinical benefits seen in motor function, there were also improvements noted in measures of activities of daily living, depressive symptoms, patients' clinical status, and aspects of quality of life such as emotional well-being, communication, and bodily discomfort (Borghain, 2014a; Borghain, 2014b; Schapira, 2017). These improvements in non-motor symptoms were seen for the 100 mg/day group in secondary measures, specifically the Parkinson's Disease Questionnaire; health status/quality of life (PDQ-39) and the Clinical Global Impression of Change in health (CGI-C) outcomes.

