7.2.1. Motor Symptoms and Non-Motor Symptoms

MDS-UPDRS (Appendix D) provides an assessment of the effects of PD on multiple aspects of a patient's life. The assessment is administered by the Principal Investigator (PI) or certified Health Care Professional (HCP) designee and consists of 4 parts:

- Part I focuses on non-motor experiences of daily living, such as mood, sleeping habits, pain, and fatigue. In IA, the investigator assesses various behaviors using information from the patient and caregiver; in IB, the assessments are completed by the patient without input from the investigator. Difficulties are rated on a 5-point scale, from 0=no problems to 4=severe problems.
- Part II is an evaluation of motor experiences of daily living, such as speech, eating, hygiene, and movement, and is completed by the patient. Difficulties are rated using the same 5-point scale as Part I.
- Part III assesses the severity of the cardinal motor findings (e.g., tremor, rigidity, bradykinesia, and postural instability). It includes 33 scores based on 18 items, and difficulties are rated using the same 5-point scale as Part I.
- Part IV is made up of questions on motor complications, and difficulties are rated using the same 5-point scale as Part I. This section integrates patient-derived information with the investigator's clinical observations and judgments and is completed by the rater (Goetz, 2008). It will be scored by the Investigator.

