8.1.1. Screening / Baseline Assessments (Visit 1, Study Day 1)

The Screening Visit and the Baseline Assessment Visit may occur on the same day. During the Screening Visit, patients who provide written consent to participate in the study and HIPAA authorization to use their personal health information will be screened for inclusion in the study according to the following procedures:

- Assessment of eligibility criteria (i.e., Inclusion [[Section 9.1](#)] and Exclusion [[Section 9.2](#)] Criteria)
- Collection of demographics and medical history information, including history of PD and other neurological conditions

For patients determined to be eligible for the study, Baseline Assessments should be conducted at the same visit that Screening occurs. If the patient requires a separate Baseline Assessment Visit, it should occur no more than 7 days after the Screening Visit.

Patients will arrive at the Investigator’s clinic in an “on” motor state. The following activities and outcome assessments (Baseline Assessments) will be completed at the clinic Baseline Visit:

- Presentation of study instructions relative to XADAGO administration, concomitant medications, reporting of safety events, patient and Care Partner (if applicable), completion of CROs and PROs, downloading and training on the eCOA system, and documentation of other study data
- Registration and training on the eCOA system (in which the patient will report PRO results)
- Assessment of concomitant medications
- MDS-UPDRS by the PI/certified HCP designee

- PDQ-39 by the patient
- MoCA by the PI/certified HCP designee
- Study Day 1 administration of XADAGO

8.1.2. Telephone Follow-up with Patient by Study Site Staff (Visit 2, Study Day 30)

All patients will be contacted by telephone on Study Day 30. If the patient is scheduled for a routine clinic visit within ± 5 days of the Study Day 30 visit, the study assessments may be performed in person with the patient during the routine clinic visit.

The following assessments will be completed:

- Review of patient information relevant to XADAGO administration and concomitant medication administration
 - Daily record (e.g., electronic diary or log) will be available for the patient to enter information relevant to XADAGO and concomitant medications taken if patient decides to utilize
- PRO assessment:
 - TSQM-9

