9.2. Exclusion Criteria

1. Any of the warnings, precautions, or contraindications listed in the Package Insert ([Appendix A](#)) that in the opinion of the PI would prevent appropriate treatment with XADAGO or impair study participation (e.g., pregnancy, lactation, severe hepatic impairment, etc.)
2. Participation in any other clinical trial of an investigational drug or device within 4 weeks prior to the Baseline Visit or at any time during this study
3. Patient is currently receiving chemotherapy or radiation for any form of cancer (if history of cancer, must be in clinical remission at study entry) or currently receiving immunotherapy
4. Patients with conditions that are likely to prevent them from accurately and reliably completing study assessments, including evidence of moderate or severe dementia as determined by the clinician (not to include mild cognitive impairment [MCI]); major psychiatric illness (specifically diagnosis of schizophrenia, bipolar disorder or a history of attempted suicide); and/or severe and progressive medical illness (including terminal cancer, end-stage renal disease +/- undergoing dialysis)
5. Severe or unpredictable dyskinesia at the time of the Baseline Visit
6. Previous participation in this study; a patient may not re-enroll after prior discontinuation or completion

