## **9. SAFETY AND TOLERABILITY**

The analysis of safety and tolerability data includes an overall summary of tolerability, adverse event preferred terms by body/organ system, drug exposure (duration of treatment) by treatment (50 mg vs 100 mg), dosing information/compliance, concomitant medications, clinical laboratory results, vital signs, physical examination, and study termination status. Tables summarizing the adverse events reported by subjects who died, experienced non-fatal serious adverse events (SAE), or prematurely discontinued the study due to adverse event (AEs) will be prepared. Summaries of potentially clinically notable laboratory results and vital sign abnormalities will be presented. Paired subject data listings will be provided to support the summaries of SAEs and these will be sorted first by subject and then by event preferred term or parameter.

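### MDS-UPDRS Part IV is rated before and after XADAGO, but the SAP uses it only in an undefined efficacy score, so rated dyskinesia is not a safety outcome

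*SAP*

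**What the plan says.** **The known harm.** Protocol 6.2, on the two placebo-controlled trials: "The most commonly reported adverse event (AE) was dyskinesia, which was significantly higher in the treatment groups versus placebo". Exclusion criterion 5 in Protocol 9.2 removes only patients with "Severe or unpredictable dyskinesia at the time of the Baseline Visit", so patients with milder dyskinesia can enter.

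**The rating.** Protocol 7.2.1 says that MDS-UPDRS "consists of 4 parts". On the last of these: "Part IV is made up of questions on motor complications, and difficulties are rated using the same 5-point scale as Part I". Protocol Table 3 schedules MDS-UPDRS at Baseline and Days 60, 90 and 180.

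**Its use in the SAP.** Section 8.4, under Efficacy: "The change in MDS-UPDRS, PDQ-39, and MoCA from the Baseline Assessment Visit to the Primary Endpoint (Study Day 60) will be summarized by cohort and" pooled, with a paired t-test for continuous endpoints. Section 6.5.4 restricts the MDS-UPDRS analysis to patients who completed the scale at Day 60. Subscales are mentioned only in section 8.1, for checking baseline distributions.

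**The safety outputs.** SAP section 9 begins: "The analysis of safety and tolerability data includes an overall summary of tolerability, adverse event preferred terms by body/organ system, drug exposure (duration of treatment" and so on). It continues with compliance, concomitant medications, laboratory results, vital signs, physical examination and termination status. Neither MDS-UPDRS nor Part IV appears there.

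**The concern.** A harm already known to be more frequent on the drug is best described against each patient's own starting level. This study appears to collect what that requires: a structured rating of motor complications before the first dose and again at follow-up. The SAP sends it only into an efficacy mean.

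That mean suits this purpose poorly however the score is built. In a total, a rise in dyskinesia is added to any fall in motor scores. In a Part IV subtotal, it may be pooled with other motor complications. Neither gives the number of patients who newly developed dyskinesia or got worse.

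The remaining source is adverse event reporting. Protocol 11.4 relies on spontaneous report, an open question or observation. Table 3 schedules no adverse event assessment at the Day 30 call, so the first scheduled enquiry is Day 60. The report could therefore show a favourable MDS-UPDRS change beside a dyskinesia count that takes no account of the Part IV ratings.

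**Working it through.** The plan states no power, effect size, SD or dyskinesia rate, so it has no figure to reproduce. The check has two steps.

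**1. Where the rating goes**

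| Question | Documents |
|---|---|
| Rated before and after first dose? | Yes: Baseline, Days 60, 90, 180 (Protocol Table 3) |
| Post-baseline analysis? | One: change to Day 60 (SAP 8.4) |
| Which score? | Not stated; by contrast, Protocol 7.2.2 specifies a sum score for PDQ-39 |
| Any safety output using it? | None in SAP 9 to 9.3 |
| Dyskinesia as an adverse event? | Tabulated by preferred term, maximum severity, relationship and cohort (SAP 9.2.1) |
| Does a Part IV rise trigger an adverse event record? | No such rule |

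**2. What a mean score would show, compared with a count**

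Inputs from the documents: up to 540 evaluable patients (SAP 4.3.1). For Part III, "It includes 33 scores based on 18 items", each rated 0 to 4, so that part alone spans 33 × 4 = 132 points.

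Assumptions, because the documents give none: a share p of 5%, 15% or 30% worsens by 2 points in total on dyskinesia items; the SD of MDS-UPDRS change is 8 to 16; the three cohorts are equal, 540 / 3 = 180 each.

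- Shift in the mean = 2 × p: 0.10, 0.30 and 0.60 points.
- Standard error = SD / √n. At n = 540: 8 / 23.24 = 0.34 and 16 / 23.24 = 0.69.
- Shift in standard errors: smallest 0.10 / 0.69 = 0.15; largest 0.60 / 0.344 = 1.74.

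| Share worsening | Shift in mean | Shift in SE (SD 16 to SD 8) | Direct count, n = 540, Wilson 95% CI |
|---|---|---|---|
| 5% (27 patients) | 0.10 | 0.15 to 0.29 | 3.5 to 7.2% |
| 15% (81) | 0.30 | 0.44 to 0.87 | 12.2 to 18.3% |
| 30% (162) | 0.60 | 0.87 to 1.74 | 26.3 to 34.0% |

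In one cohort of 180, 15% (27 patients) has a 95% CI of 10.5 to 20.9%.

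Other assumptions lead to the same place. With 5% to 20% of patients worsening by 1 to 4 points, the shift is 0.05 × 1 = 0.05 to 0.20 × 4 = 0.80. If a total were used, an assumed mean motor change of −3 would then be reported as −2.95 to −2.20. A reader could not tell that any of the difference was dyskinesia.

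**The case against.** **Netting is not planned text.** SAP 8.4 does not say that a total is used. A reader might infer that the SAP sets dyskinesia against motor benefit by design; the documents do not support that. If parts are analysed separately, the 132-point span of Part III is irrelevant. This stands: offsetting is possible, not planned.

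**Dyskinesia does reach the safety tables.** Protocol 11.2.1 counts deterioration of an existing condition as an adverse event, observed events are recorded, and the staff who rate MDS-UPDRS also assess adverse events at Days 60, 90 and 180. It would be wrong to say that dyskinesia is never reported as a harm. Only the rating is unused. Still, nothing links a higher rating to an event record, and event tables do not show change from a rated baseline.

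**Part IV's items are not visible.** The main text says motor complications, and Appendix D is not in the text reviewed. This stands: both the dyskinesia items and any pooling with other complications must be confirmed there.

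**The protocol does not call dyskinesia the main or only harm.** Correct. The same section says that safety profiles resembled placebo, and that 1% of treated patients against 0% on placebo stopped because of dyskinesia.

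**Protocol 12.1 promises descriptive statistics for all data collected.** That is general; SAP sections 8 and 9 do not turn it into a dyskinesia output.

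**Safety is not the principal objective, and the arithmetic rests on assumptions.** Both true. Any few items in a large composite move its mean little. The calculation shows only that a mean is a poor summary of a harm affecting a minority.

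**Conclusion.** The point holds in this form: SAP 8.4 does not define the MDS-UPDRS score and plans no separate Part IV or dyskinesia summary, and no safety output uses the rating. Apart from recorded adverse events, systematically rated dyskinesia is not reported as a safety outcome.

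No number in the plan is contradicted. The size is illustrative: under the assumed rates and SDs, the mean moves by 0.1 to 0.6 points (0.15 to 1.7 standard errors at n = 540), whereas a count would carry a 95% CI about 4 to 8 percentage points wide. The conclusion also rests on Part IV containing dyskinesia items, which Appendix D must confirm.

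A reader might also infer that the adverse event count will be too low. Reporting by open question makes that plausible, but the documents offer no figure to establish it. Nor would the rated percentage be a rate caused by XADAGO: there is no control group, Cohorts A and B also changed other Parkinson's drugs, and patients may stop XADAGO and remain in the study (Protocol 10.1.4).

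This is an inexpensive improvement that the sponsor should make.

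**What to change.** 1. In SAP 8.4, state that each MDS-UPDRS part is summarised separately, and that a favourable change is to be read with the table below.
2. Confirm the dyskinesia items in Appendix D. Then add to SAP 9 a descriptive table, by cohort and overall, with the Baseline-to-Day 60 shift and the number and percentage (95% CI) of patients with new dyskinesia (0 at Baseline, at least 1 later) or worsened dyskinesia (any item at least 1 point higher). The shift table lets readers judge whether one-point rises could be rating variability.
3. Base it on safety-population patients with a Baseline and a post-baseline rating, using observed ratings. Day 60 is the first post-baseline MDS-UPDRS, so carrying the last value forward to it would score a missing patient as unchanged. Report how many have no Day 60 rating, since early leavers may include patients troubled by dyskinesia, and how many had stopped XADAGO by then.
4. Show the table beside the dyskinesia adverse event count.
5. Repeat it at Days 90 and 180 for the Extension data available at database lock. SAP 5.2 locks after the last patient's Visit 3, so these data may be incomplete and should be labelled so.

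Cost: SAP wording and one extra table from data already collected, with no new visits or procedures and no change to treatment. The downside is that the rated percentage will probably exceed the adverse event percentage, and it is descriptive only.
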